9. Any ongoing anticancer therapy including; small molecules, immunotherapy, chemotherapy, monoclonal antibodies, radiation (curative/treatment intent) or any other experimental drug. Prior therapy must be stopped within four weeks before first infusion in the study, or 5 half-lives, or twice the duration of the biological effect of the investigational product (whichever is shortest). Adjuvant anti-hormonal treatment(s) for previously treated breast cancer or prostate cancer are allowed. Bisphosphonates are allowed, Denosumab and other RANK ligand inhibitors are prohibited. Note that palliative radiation only requires a two week washout.
10. Known current malignancy other than inclusion diagnosis. Prior curable cancer with complete remission for >2 years is allowed.
11. Any other ongoing significant, uncontrolled medical condition as per Investigator discretion.
12. Received a live vaccine within 30 days prior to first dose of study drug.
13. Clinically significant active viral, bacterial or fungal infection requiring:
 - a. Intravenous treatment with antimicrobial therapy completed less than two weeks prior to first dose, or
 - b. Oral treatment with antimicrobial therapy completed less than one week prior to first dose.Prophylactic treatment with antibiotics (e.g. for dental extractions) is allowed.
14. Known positive serology for human immunodeficiency virus (HIV), hepatitis B, or hepatitis C (except in cases of immunity after cured infection). Testing not required.

15. Substance abuse, medical, psychological or social conditions that may interfere with the patient's participation in the trial or evaluation of the trial result in the opinion of the Investigator.
16. Women who are pregnant or breast feeding.

Test product, dose and mode of administration:

Each patient will be administered separate intradermal injections (at the same injection sites) of HS-130 (Lot HBI-HS-130-FP-001: OX40L-Ig concentration = 338 ng OX40L-Ig/10⁶ cells/24-hr) and HS-110 (Lot 0000748931: gp96-Ig concentration = 104 ng gp96-Ig/10⁶ cells/24-hr) based on the dose levels as defined in the dose escalation scheme (Section 6.1.1) on Day 1 of each cycle.

Dose-limiting toxicity (DLT):

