6.0 TREATMENT OF SUBJECTS

6.1 Drug Preparation and Administration

Both HS-130 and HS-110 drug products will be administered via intradermal injections/re-injections based on the dose levels as defined in the dose escalation scheme (Section 6.1.1) on Day 1 of each cycle.

If any serious adverse reaction occurs these may be treated per institutional practice, as noted in Section 6.4 Concomitant Medication.

The HS-130 final drug product is packaged in single-dose vials as fully-diluted frozen liquid filled under aseptic conditions in 1.2 mL cryovials, containing 0.6 mL suspension of 2×10^7 cells/mL (targeted) in a cryopreservative buffer, with a final formulation of 0.567% sodium chloride, 0.5% human serum albumin (HSA), 0.007% sodium bicarbonate, 6% pentastarch, and 5% dimethyl sulfoxide (DMSO).

HS-110 (viagenpumatulcel-L) is packaged in single-dose vials as fully-diluted frozen liquid filled under aseptic conditions in 1.2 mL cryovials, containing 0.6 mL suspension of 2×10^7 cell/mL (targeted) in a cryopreservative buffer, with a final formulation of 0.567% sodium chloride, 0.5% HSA, 0.007% sodium bicarbonate, 6% pentastarch, and 5% DMSO.

Each patient will be administered up to a total of 10 spatially divided intradermal injections/re-injections of ≤ 0.14 mL per injection, depending on the required HS-130 and HS-110 dose levels. HS-130 will be injected first, and a period of no less than 2 minutes, but no more than 5 minutes, should elapse before administering HS-110. HS-110 must be injected into the same exact location as the HS-130 injections (re-injected sites). There are some dose levels (3, 5, 6, and 7) where the number of HS-110 injections will exceed the number of HS-130 injections. In these cases, after all HS-130 sites have been re-injected, the HS-110 may be administered in a new spatially divided injection site.

At each cycle, the injection region will alternate between the left shoulder and right shoulder. The HS-130 and HS-110 injections will all be administered into the designated injection region for that cycle (left shoulder or right shoulder) to increase volume distribution and enhance antigen presentation to lymph node regions.

Table 1: HS-130/HS-110 Dose Administration Guidelines

Dose Level	Study Drug	Total mL	Volume (mL) per Injection							
			Injection #1	Injection #2	Injection #3	Injection #4	Injection #5	Injection #6	Injection #7	
-1	HS-130	0.02	0.02							
	HS-110	0.06	0.06							
1	HS-130	0.04	0.04							

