	HS-110	0.10	0.10							
2	HS-130	0.10	0.10							
	HS-110	0.10	0.10							
3	HS-130	0.10	0.10							
	HS-110	0.22	0.12	0.10						
4	HS-130	0.18	0.10	0.08						
	HS-110	0.22	0.12	0.10						
5	HS-130	0.18	0.10	0.08						
	HS-110	0.44	0.12	0.12	0.10	0.10				
6	HS-130	0.36	0.12	0.12	0.12					
	HS-110	0.44	0.12	0.12	0.10	0.10				
7	HS-130	0.36	0.12	0.12	0.12					
	HS-110	0.86	0.14	0.12	0.12	0.12	0.12	0.12	0.12	0.12

Drug products will be supplied to clinical sites via shipments in liquid nitrogen dry-shipper units, which will be validated to maintain cryogenic temperatures for up to 10 days. Upon arrival, the products will be transferred to controlled liquid nitrogen storage at the clinical site in the liquid nitrogen vapor phase until ready for preparation. Study staff must take care to minimize temperature excursions during transfer of the product from shipping containers to controlled liquid nitrogen storage on site.

Drug products will not be retrieved from cryogenic storage until the study subject is present and available for dosing. When removing a product carton from storage to retrieve a vial for dosing, any doses remaining in the carton will be returned to cryogenic storage immediately. Study drugs must be administered within 2 hours of retrieval from the dewar (cryogenic storage).

Stability studies for HS-130 are currently ongoing and clinical sites will be notified of storage information and/or shelf life change. The instructions for preparation, administration, stability and storage of HS-110 to be used in combination with HS-130 will reference instructions per the Investigational Product Manual.

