6.1.1 Dose Escalation Scheme

Escalating doses of the viable, replication-incompetent, human whole cell vaccines, HS-130 and HS-110 will be administered to patients via intradermal injections/re-injections (up to 10 total) on Day 1 of a two-

week cycle. The length of each cycle is two weeks, and the DLT window of observation includes the safety data obtained from the first two treatment cycles, Cycle 1 and Cycle 2 (4 weeks).

Seven dose levels will be explored, and patients will receive separate escalating doses of HS-130 and HS-110 in alternating fixed 1:1 or 2:1 ratio based on the amount of secreted OX40L-Ig (HS-130) and gp96-Ig fusion protein (HS-110) per cell of the drug product. The starting dose of HS-130/HS-110 combination is based on the dose-ranging studies conducted in animal models of T cell expansion and tumor challenge, as well as established clinical experience from HS-110.

Table 2: HS-130/HS-110 Dose Levels

Cohort	Dose level	HS-130 dose* (ng/24-hr OX40L-Ig)	HS-110 dose* (ng/24-hr gp96-Ig)	HS-130: HS-110 Ratio	Total number of AD100 cells (Q2W) [#]	Minimum number of patients
1	-1	75 ng/24-hr	75 ng/24-hr	1:1	1.0 million	1
	1	150 ng/24-hr	150 ng/24-hr	1:1	1.9 million	1
	2	300 ng/24-hr	150 ng/24-hr	2:1	2.3 million	1
	3	300 ng/24-hr	300 ng/24-hr	1:1	3.8 million	1
	4	600 ng/24-hr	300 ng/24-hr	2:1	4.7 million	1
2	5	600 ng/24-hr	600 ng/24-hr	1:1	7.6 million	3
3	6	1,200 ng/24-hr	600 ng/24-hr	2:1	9.3 million	3
4	7	1,200 ng/24-hr	1,200 ng/24-hr	1:1	15.1 million	3

*The number of cells administered to achieve the HS-130 (ng/24-hr of OX40L-Ig protein) and HS-110 (ng/24-hr of gp96-Ig protein) dose will be determined based on the specifications for that batch of the drug product. For HS-130: Lot HBI-HS-130-FP-001 = 241 fg/cell/24-hr and HS-110: Lot 0000748931 = 104 fg/cell/24-hr. The productivity per cell will be determined using the same assay format and standards for pre-clinical and clinical derived material.

[#] The suggested total number of allogeneic tumor cells (AD100) administered every second week at the highest dose level is similar to or less than the weekly dose of 10 million HS-110 cells that has been established safe and immunologically effective in the HS-110 study (NCT02439450, IND No. 14814).

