The first cohort will employ an accelerated design to evaluate the first 4 dose levels in single patients. There will be a staggered enrollment with a minimum 1-week delay between each patient in cohort 1. If any drug-related \geq Grade 2 (other than Grade 2 injection site reaction with pain) event occurs during the first cycle of treatment, the study will revert to 3+3 design starting at that dose level.

Subsequent cohorts in the dose escalation phase will enroll patients following the standard 3+3 design. Three patients will be enrolled in each subsequent dose cohort and enrolled with a (minimum) 1-week staggered delay (i.e. Patient 2 to be dosed \geq 1-week after Patient 1 received the first dose, and Patient 3 to be dosed \geq 1-week after Patient 2 received the first dose).

In the 3-patient cohorts (i.e. 3 patients treated at the same dose), if 1 out of 3 patients experience a DLT during the first two treatment cycles, the dose cohort will be expanded up to 6 patients. If \geq 2 out of 6 patients experience DLTs, the MTD has been exceeded, and dose escalation will cease. Up to 3 additional patients will be enrolled at the next lowest dose if only 3 patients were treated at that dose level, to confirm safety of that dose. If a DLT is observed already with the first patient in Cohort 1, the Safety Review

Committee (Section 8.1.2.8.1) may suggest and approve a dose de-escalation cohort with at least 50 % reduction of HS-110 and HS-130 (dose level -1).

Once all patients in a cohort have completed the first two cycles of dosing and received at least 2 doses of HS-130/HS-110, the safety and tolerability of the combination treatment administered will be reviewed by the safety review committee (SRC). If 0 out of 3 patients or 1 out of 6 patients experience a DLT, then the SRC may recommend enrollment at the next higher dose level.

Any patient who does not receive two doses of the study treatment during the DLT window of observation (first 2 cycles/4 weeks), for reasons other than study drug-related toxicity and did not experience a DLT will not be taken into account in the assessment of the overall DLT rate for the particular dose level cohort and will be replaced.

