8.1.2.8 Safety Data Review

8.1.2.8.1 Safety Review Committee

A Safety Review Committee (SRC) comprises of 3 members – one Investigator, a representative from Heat Biologics and the Medical Monitor will evaluate the data obtained at each dose level including a review of all adverse events (serious and non-serious adverse events) as they are reported by the study site. The SRC will recommend whether the dose should be escalated as per protocol, revised to a lower level or

intermediate level, halted altogether or more patients are required at the same dose level to evaluate safety. If a DLT is observed already with the first patient treated in Cohort 1, the SRC may suggest and approve dose de-escalation with at least 50% reduction of HS-130 and HS-110 (dose level -1), depending on the nature of the reaction.

Ad-hoc SRC meetings may be called for by both the SRC and Sponsor any time during the study if DLTs are observed and/or new safety data warrants immediate action to the conduct of the trial (including events defined by the Study Stopping Criteria in Section 5.5).

The conclusion of the SRC meeting will be documented in meeting minutes. The outcome of the SRC meeting will be communicated to all Investigators.

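### Table 1 cuts HS-110 by 40% at dose level -1 where the text requires at least 50%, two HS-130 steps miss the planned doubling, and one HS-130 lot carries two potencies

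*Combined protocol and SAP*

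**What the plan says.** **De-escalation rule.** If the first patient in Cohort 1 has a DLT, Section 6.1.1 lets the Safety Review Committee open a "dose de-escalation cohort with at least 50 % reduction of HS-110 and HS-130 (dose level -1"). Section 8.1.2.8.1 repeats the rule: the committee may "approve dose de-escalation with at least 50% reduction of HS-130 and HS-110 (dose level -1"). Both texts set a floor, and both apply it to each product.

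**Dose levels.** Section 6.1.1 describes "separate escalating doses of HS-130 and HS-110 in alternating fixed 1:1 or 2:1 ratio". Table 2 gives 75/75 ng/24-hr (HS-130/HS-110) at level -1, 150/150 at level 1, 300/150 at level 2, 300/300 at level 3 and 600/300 at level 4. HS-130 is therefore meant to double from level 1 to 2 and again from level 3 to 4.

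**Volumes.** Table 1 in Section 6.1 converts these levels to mL. HS-130 is 0.02, 0.04, 0.10, 0.10 and 0.18 mL at levels -1, 1, 2, 3 and 4. HS-110 is 0.06 mL at level -1 and 0.10 mL at level 1.

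**Potency.** The Table 2 footnote says "For HS-130: Lot HBI-HS-130-FP-001 = 241 fg/cell/24-hr". The synopsis, under the test product heading, says "Lot HBI-HS-130-FP-001: OX40L-Ig concentration = 338 ng OX40L-Ig" per 10^6 cells per 24 hours. Both statements name the same lot. HS-110 is 104 in both places.

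**The concern.** Table 1 is what a site would use to draw up the dose, and it does not reproduce the reduction that the text requires or the steps that Table 2 plans. Level -1 exists for the moment after a DLT in the first patient of a first-in-human combination, so that is where a true halving matters most. The larger HS-130 step falls in the single-patient phase, for a product with no previous human exposure (Section 2.4).

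The potency conflict is a separate matter. Doses are defined in ng/24-hr, and the RP2D is a primary objective. With two potencies printed for one lot, the number of HS-130 cells behind each ng figure cannot be established from the protocol.

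**Working it through.** **1. Level -1 against the 50% floor** (Table 1). Within one lot, dose = volume × concentration × potency, and the last two cancel in a ratio.
- HS-110: 1 − 0.06/0.10 = 40%. The floor is missed.
- HS-130: 1 − 0.02/0.04 = 50%. The floor is met.
- Table 2, either product: 1 − 75/150 = 50%.

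**2. HS-130 steps** (Table 1 volumes against Table 2 doses).
- Level 1 to 2: 0.10/0.04 = 2.5-fold; planned 300/150 = 2.0.
- Level 3 to 4: 0.18/0.10 = 1.8-fold; planned 600/300 = 2.0.
- Level 5 to 6: 0.36/0.18 = 2.0-fold; planned 1,200/600 = 2.0.

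**3. Where the volumes appear to come from.** Halve down from the level 7 totals.
- HS-110: 0.86, 0.43, 0.215, 0.1075, 0.054 mL. Table 1 prints 0.86, 0.44, 0.22, 0.10, 0.06.
- HS-130: 0.36, 0.18, 0.09, 0.045, 0.0225 mL. Table 1 prints 0.36, 0.18, 0.10, 0.04, 0.02.

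This is consistent with rounding to 0.02 mL. The deviations in steps 1 and 2 arise because neighbouring entries moved in opposite directions (0.1075 down and 0.054 up; 0.045 down and 0.09 up) or only one of them moved (0.09 up, 0.18 unchanged).

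**4. Cell totals in Table 2.** Units: 338 ng per 10^6 cells = 338 fg/cell. Formula: million cells = HS-130 ng / HS-130 potency + HS-110 ng / 104. Example, level 7: 1,200/338 + 1,200/104 = 3.55 + 11.54 = 15.09; with 241, 4.98 + 11.54 = 16.52.

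| Level | Printed | With 338 | With 241 |
|---|---|---|---|
| -1 | 1.0 | 0.94 | 1.03 |
| 1 | 1.9 | 1.89 | 2.06 |
| 2 | 2.3 | 2.33 | 2.69 |
| 3 | 3.8 | 3.77 | 4.13 |
| 4 | 4.7 | 4.66 | 5.37 |
| 5 | 7.6 | 7.54 | 8.26 |
| 6 | 9.3 | 9.32 | 10.75 |
| 7 | 15.1 | 15.09 | 16.52 |

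At levels 1 to 7 the printed totals reproduce with 338 to within about 1.3%. With 241, the value in the table's own footnote, the calculated totals are 8.7% to 16.8% higher than those printed. Level -1 does not discriminate: 1.0 is near 1.03 (241), but it is also about half of the rounded 1.9. Potency ratio: 338/241 = 1.40.

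**The case against.** The strongest defence is that steps 1 and 2 are a single rounding effect. Table 2 defines the dose and halves both products exactly; Table 1 offers administration guidelines in volumes that a syringe can measure. The HS-110 gap at level -1 is 0.01 mL of a product already given in over 1,000 doses. Level -1 opens only if the committee chooses it, and the committee may also set a lower or intermediate level. The cell totals drive no decision, since the MTD rests on DLT counts. At level 7, 15.1 and 16.5 million every two weeks are both below the 20 million (2 × 10 million) that weekly HS-110 dosing gives over the same period.

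Most of this stands, and it limits the weight of the point. It does not remove it. The protocol states no rounding rule or tolerance, and rounding cannot excuse missing a requirement worded as a minimum. Nor does rounding explain 338 against 241. The footnote says that cell numbers "will be determined based on the specifications for that batch of the drug product", but both potencies are given for the same batch, so that wording does not reconcile them.

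A reader might go further and infer that Table 1 overdoses patients, by multiplying its volumes by the nominal fill concentration. The documents do not support that. The fill figure is given only as "cell/mL (targeted) in a cryopreservative buffer", and no usable concentration is stated for either lot. It may be in the separate manual: the preparation of "HS-110 to be used in combination with HS-130 will reference instructions per the Investigational Product Manual". A lower, unstated concentration fits every Table 1 volume to within 0.01 mL: 13.26 to 13.42 million/mL for HS-110, and for HS-130 either 13.46 to 13.83 (at 241) or 9.60 to 9.86 (at 338). Because both HS-130 fits work, the volumes do not show which potency is right either.

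**Conclusion.** Wrong as written, on three counts.

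- Table 1 reduces HS-110 by 40% at level -1 against a stated minimum of 50%.
- HS-130 steps are 2.5-fold (level 1 to 2) and 1.8-fold (level 3 to 4) against a planned 2-fold.
- One HS-130 lot has two potencies that differ 1.40-fold, and Table 2 at levels 1 to 7 does not follow its own footnote.

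The first two rest only on the compared doses coming from the same lot at one concentration. The third rests on both statements naming the same lot. Rounding to 0.02 mL as the cause is an inference. The volume gaps are about 0.01 mL, so this is an inexpensive correction that should be made and not a demonstrated hazard. Neither overdosing nor the correct potency can be read from the documents.

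**What to change.** In Table 1:
- Set HS-110 at level -1 to 0.05 mL (1 − 0.05/0.10 = 50%).
- Set HS-130 at levels 2 and 3 to 0.09 mL, so that level 3 to 4 is 0.18/0.09 = 2.0-fold.
- Set HS-130 at level 1 to 0.045 mL if the syringe allows (0.09/0.045 = 2.0-fold). If it stays at 0.04 mL, the level 1 to 2 step is 0.09/0.04 = 2.25-fold, and the protocol should say so.
- If level 1 becomes 0.045 mL, keep HS-130 at level -1 at or below 0.0225 mL. The present 0.02 mL complies (1 − 0.02/0.045 = 56%).

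In the synopsis and the Table 2 footnote, state one potency for lot HBI-HS-130-FP-001. Recompute the Table 2 cell column from it, and the Table 1 volumes if they are affected.

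The cost is a table and footnote amendment and finer syringe graduations (0.01 mL, or 0.005 mL for the exact doubling). No patients or procedures are added.

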6.1.2 Dose-Limiting Toxicity

Adverse events will be assessed per CTCAE version 5. Any toxicity that is at least possibly related to the study drug may be considered as a DLT, which is defined as non-acceptable (as defined below) treatment related toxicity (i.e., not attributable to the active disease, disease-related processes under investigation or intercurrent illness) observed during the first 4 weeks (or Cycle 1 and Cycle 2) of study treatment. Ongoing safety events beyond Cycle 2 will be reviewed across all cohorts during the study to help inform dose escalation decisions. Note, that all patients who enrolled in the study will be included in assessment of DLT.

DLT is defined as non-acceptable toxicity which includes:

1. Hematological toxicities \geq Grade 3.
2. Non-hematological toxicity \geq Grade 3.
3. Autoimmunity \geq Grade 3
4. Any other toxicity (greater than at baseline), considered clinically significant and/or unacceptable, and that does not respond to supportive care and results in a disruption of the dosing schedule of more than 14 days.

DLT excludes:

1. Hematological and non-hematological \leq Grade 2 unless considered non-acceptable.
2. Grade 3 self-limited or medically controllable toxicities (e.g., fever without \geq Grade 3 neutropenia, nausea, vomiting, diarrhea, fatigue).
3. Electrolyte disturbances that are managed to Grade 1 or less with supplemental therapy.

A DLT will be considered related to HS-130/HS-110 treatment unless there is a clear, well-documented, alternative explanation for the AE. AEs that meet the above criteria, but occur after the DLT window of observation will not be defined as DLTs, but will be reported as AEs/Serious Adverse Events (SAEs), as applicable, and will be reviewed across all cohorts during the study to help inform dose escalation decisions.

In case of suspicion of a DLT, the Investigator must inform the Medical Monitor/Sponsor immediately. The DLT will be confirmed by the Medical Monitor/Sponsor and a decision must be taken by the Sponsor regarding if an *ad hoc* SRC meeting is required.

Patients who are tolerating HS-130/HS-110 will not have to discontinue dosing prematurely due to the

occurrence of DLTs in another patient in the same cohort, unless decided by the SRC. If requested by the Investigator, depending on the nature of the DLT and patient status, the SRC and the Sponsor may allow a patient to continue with study treatment at a reduced dose.

6.1.3 Maximum Tolerated Dose (MTD) and Recommended Phase 2 Dose (RP2D)

The definition of MTD will be based upon review of safety data and DLTs corresponding to the first two cycles of therapy in at least 6 evaluable patients. MTD will be defined as a dose where 0 or 1 out of 6 patients have DLTs. The RP2D may be equivalent to MTD OR the maximum feasible dose. The dose that is selected after this study for phase 2 evaluation may also be an immunologically active dose (assessed based on flow cytometry analysis of blood, using immune marker panels of activation and suppression as defined in Section 8.6.1).

6.2 Dose Interruptions/Withholding

Study drug may be withheld from a patient based on the Investigator's decision in the event of intercurrent illness, adverse event, administrative reasons, or other reasons. If the patient's condition subsequently improves, or the situation that resulted in withholding study drug rectifies itself, the Investigator may resume dosing as soon as possible, unless the delay is more than 2-weeks. Doses should not be skipped.

Dosing should be delayed for any DLT-equivalent toxicity and possible >Grade 2 adverse events considered related to study medication. At the Investigator's discretion, dosing may recommence when the toxicity has resolved to Grade 2 or less. Immune related reactions or allergy should resolve to Grade 1 or less.

Treatment will be discontinued if the next cycle cannot be initiated if a TEAE has not resolved (to acceptable grade) after ≤ 2 weeks.

Patients who miss a dose during Cycle 1 and Cycle 2 may be replaced in the study per Section 5.4.2. The interruption and/or missed dose(s) should be recorded.

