Adverse events will be assessed per CTCAE version 5. Any toxicity that is at least possibly related to the study drug may be considered as a DLT, which is defined as non-acceptable (as defined below) treatment related toxicity (i.e., not attributable to the active disease, disease-related processes under investigation or intercurrent illness) observed during the first 4 weeks (or Cycle 1 and Cycle 2) of study treatment. Ongoing safety events beyond Cycle 2 will be reviewed across all cohorts during the study to help inform dose escalation decisions. Note, that all patients who enrolled in the study will be included in assessment of DLT.

DLT is defined as non-acceptable toxicity which includes:

1. Hematological toxicities \geq Grade 3.
2. Non-hematological toxicity \geq Grade 3.
3. Autoimmunity \geq Grade 3
4. Any other toxicity (greater than at baseline), considered clinically significant and/or unacceptable, and that does not respond to supportive care and results in a disruption of the dosing schedule of more than 14 days.

DLT excludes:

1. Hematological and non-hematological \leq Grade 2 unless considered non-acceptable.
2. Grade 3 self-limited or medically controllable toxicities (e.g., fever without \geq Grade 3 neutropenia, nausea, vomiting, diarrhea, fatigue).
3. Electrolyte disturbances that are managed to Grade 1 or less with supplemental therapy.

A DLT will be considered related to HS-130/HS-110 treatment unless there is a clear, well-documented, alternative explanation for the AE. AEs that meet the above criteria but occur after the DLT window of observation will not be defined as DLTs, but will be reported as AEs/Serious Adverse Events (SAEs), as applicable, and will be reviewed across all cohorts during the study to help inform dose escalation decisions.

In case of suspicion of a DLT, the Investigator must inform the Medical Monitor/Sponsor immediately. The DLT will be confirmed by the Medical Monitor/Sponsor and a decision must be taken by the Sponsor regarding if an *ad hoc* SRC meeting is required.

Patients who are tolerating HS-130/HS-110 will not have to discontinue dosing prematurely due to the occurrence of DLTs in another patient in the same cohort, unless decided by the SRC. If requested by the Investigator, depending on the nature of the DLT and patient status, the SRC and the Sponsor may allow a patient to continue with study treatment at a reduced dose.

Safety Review Committee (SRC)

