6.3 Dose Modification

One level dose reduction per the dose escalation scheme, for toxicity is allowed. If the toxicity is equivalent to a DLT (see Section 6.1.2) then continued treatment at a lower dose level needs approval by the sponsor and/or SRC.

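### Section 6.2 leaves re-dosing after a DLT-equivalent toxicity to the Investigator, with no dose or approver named, in conflict with 6.1.2 and 6.3

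*Combined protocol and SAP*

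**What the plan says.** Section 6.2 opens its toxicity rule with "Dosing should be delayed for any DLT-equivalent toxicity and possible >Grade 2 adverse events considered related to study medication". The next sentence is "At the Investigator's discretion, dosing may recommence when the toxicity has resolved to Grade 2 or less". Immune-related or allergic reactions must come down to Grade 1 or less. The same section sets the outer limit on any interruption: "the Investigator may resume dosing as soon as possible, unless the delay is more than 2-weeks".

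Section 6.1.2, repeated in the synopsis, deals with a patient who has had a DLT. If the Investigator asks, and depending on the event and the patient, "the SRC and the Sponsor may allow a patient to continue with study treatment at a reduced dose".

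Section 6.3 says "One level dose reduction per the dose escalation scheme, for toxicity is allowed". Where the toxicity is equivalent to a DLT, "then continued treatment at a lower dose level needs approval by the sponsor and/or SRC".

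Three other places bear on the point. Section 6.1.2 describes a DLT as non-acceptable toxicity in the first 4 weeks, and says that later events meeting the same criteria are not called DLTs. Section 4.4 and the synopsis make continuing at the same dose after Cycle 2 conditional on there being no unacceptable toxicity. Section 5.4 lists unacceptable adverse events among the reasons to stop therapy.

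**The concern.** The sections give different answers to one practical question: after a DLT-equivalent toxicity has settled, who may give the next dose, and how much? A site following 6.2 alone could re-dose at the full assigned dose without asking anyone. A site following 6.1.2 would wait for the SRC and the Sponsor and then reduce. Section 6.3 adds an odd asymmetry, because approval attaches to the restart with less exposure and not to the one with more.

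What is at stake is the safety of the individual patient on re-exposure. HS-130 has not been given to humans before (section 2.4), and no formal GLP toxicology studies have been conducted (section 2.3.2).

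**Working it through.** The plan gives no figure to reproduce, so the check is a comparison of texts.

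**1. Does the discretion sentence reach DLT-equivalent events?** Yes. It directly follows the sentence that delays dosing for DLT-equivalent toxicity and for related events above Grade 2. The toxicity it mentions can only be one of those just named, and no carve-out is made.

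**2. Who decides, and at what dose?**

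| Restart | 6.2 | 6.1.2 and synopsis | 6.3 |
|---|---|---|---|
| In the 4-week window, reduced dose | Investigator | SRC and Sponsor | Sponsor and/or SRC |
| In the window, same dose | Investigator | Only a reduced dose is offered | Silent |
| After the window, reduced dose | Investigator | Does not apply by its terms | Sponsor and/or SRC |
| After the window, same dose | Investigator | Does not apply by its terms | Silent |

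The two reduced-dose rows conflict on who decides. In the window, 6.1.2 and 6.3 also differ from each other on the approver. In the same-dose rows only 6.2 gives an answer. The last row is the weakest, because 6.3 has no time limit but asks for approval only at a lower level.

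**3. Is a same-dose restart barred elsewhere?** Sections 4.4 and 5.4, read with the definition of a DLT as non-acceptable toxicity, point that way. They cannot be an automatic bar. If every DLT-equivalent event counted as an unacceptable adverse event under 5.4, therapy would have to stop, and the reduced-dose continuation in 6.1.2 and 6.3 could never happen. Section 4.4 also starts only once two cycles are complete, so it does not govern the second dose after a Cycle 1 event. By contrast, section 4.1 states an express bar for treatment beyond progression: no DLT, and toxicities back to baseline.

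**4. Which events are affected?** An event must pass every filter:
- It meets the DLT criteria. Criterion 4 drops out, because it needs a dosing disruption of more than 14 days and 6.2 allows no restart after more than 2 weeks (2 × 7 = 14 days). Criteria 1 to 3, Grade 3 or higher, remain.
- It is not excluded in 6.1.2. Grade 3 events that are self-limited or medically controllable are excluded, as are corrected electrolyte disturbances.
- It resolves to Grade 2 or less (Grade 1 or less if immune-related or allergic) within the 2-week limit.

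What is left is mainly Grade 4 events, and Grade 3 events that were neither self-limited nor controllable but still recovered in time. The documents give no rate for these, and none is assumed.

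**5. What does one level down mean?** From Table 2 (ng/24-hr):

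| Step | HS-130 | HS-110 |
|---|---|---|
| 7 to 6 | 1,200 to 1,200 | 1,200 to 600 |
| 6 to 5 | 1,200 to 600 | 600 to 600 |
| 5 to 4 | 600 to 600 | 600 to 300 |
| 4 to 3 | 600 to 300 | 300 to 300 |
| 3 to 2 | 300 to 300 | 300 to 150 |
| 2 to 1 | 300 to 150 | 150 to 150 |
| 1 to -1 | 150 to 75 | 150 to 75 |

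From levels 3, 5 and 7, a one-level reduction leaves HS-130, the new product, unchanged. This does not measure the conflict, but it matters for the fix.

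**The case against.** The best defence is that the sections divide the work. Section 6.2 concerns interruptions, so it sets timing: when to hold, the grade to wait for, the longest delay. Section 6.3, immediately after it, concerns dose and approval. On that reading 6.2 is silent on dose because dose is handled next door. The reading is available, but the protocol never states it, and the words about the Investigator's discretion say who decides, not only when.

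A second defence is that the default after a DLT is to stop, with 6.1.2 and 6.3 as the only exceptions, both at a lower dose. This stands in part: it is the likely intent, and it limits how far the literal reading should be pressed. It is still inference, for the reasons in step 3.

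It is also fair that 6.1.2 is worded as a permission, and that the Investigator is not acting unseen. A suspected DLT must be reported at once to the Medical Monitor/Sponsor, who confirm it, and the SRC reviews adverse events as they are reported. None of these is an approval before re-dosing. The section 5.5 stop needs a related death or at least two related Grade 4 events, so a single DLT need not trigger it.

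A reader might infer that the protocol sanctions same-dose re-challenge after a DLT. It does not: 6.2 names no dose, and 4.4, 5.4 and 6.1.2 lean the other way. A reader might also infer that every DLT-equivalent event after the window must lead to a dose reduction. The documents do not support that either. Section 6.1.2 does not call those events DLTs, and 6.3 makes the one-level reduction optional.

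**Conclusion.** The protocol is wrong as written on this point, in the sense of an internal conflict. Section 6.2 gives the restart decision after a DLT-equivalent toxicity to the Investigator with no dose or approver. Sections 6.1.2 and 6.3 place it with the SRC and the Sponsor, or with either, and only at a lower dose. Read literally, a same-dose restart is neither expressly barred nor subject to approval.

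The size is small, and the point ranks as a minor safety clarification. Few events can pass all the filters in step 4. Counting doses given after week 4 would show where the 6.1.2 sentence no longer applies, but not how many patients are at risk, so no such figure is offered. A reader might suspect that the dose-finding result is compromised. It is not: the event has already been counted before any restart, and the DLT definition, the MTD definition and the escalation rules are untouched.

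The conclusion assumes that a site reads 6.2 as it stands, without supplying the unstated timing-only interpretation.

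**What to change.** - **Section 6.2:** limit the Investigator-discretion sentence to related events above Grade 2 that are not DLT-equivalent. Add that any re-dosing after a DLT in the window, or a DLT-equivalent toxicity after it, needs documented prior approval under 6.1.2/6.3, whatever the dose.
- **Section 6.3:** extend the approval requirement from lower-dose continuation to any re-dosing after such an event.
- **Dose:** for in-window DLTs, keep the reduced dose that 6.1.2 already sets. For later events, let the approver set the dose. Mandatory reduction there would be a new restriction, and Table 2 has no level below -1 to reduce to.
- **Approver:** use one wording in 6.1.2, the synopsis and 6.3. The choice is the sponsor's.
- **Record:** have each approval state both the HS-130 and the HS-110 restart dose, since one level down may change only one of them.

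The cost is a few sentences, with no added patients or procedures. The downside is the sign-off. The next dose is due 14 days after the last and may slip by at most 14, so approval must arrive by day 14 + 14 = 28 after the last dose, or a recovered patient loses treatment. The and/or approver wording in 6.3 reduces that risk.
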